13.2.3 Summary of planned analyses

The differences in primary outcomes (SCORE risk and Framingham Risk Score) at one year between the treatment groups will be measured and analysed using t-test, for a detailed statistical analyses plan see Appendix 4. As the group sizes are large (more than thousand), it is valid to assume normal distribution of the error around the mean value estimates in both the intervention and the control group. A two-sided p-value <0.05 will be regarded as statistically significant. Complementary to the absolute difference in the Score and the statistical testing of hypotheses, Cohen's effect size will be derived for the difference in mean outcome values divided by a pooled standard deviation of the Score between the 2 groups.

In sensitivity analyses, we will conduct a linear regression covariate-adjusted analysis. We will use the continuous form of the primary outcomes (SCORE risk and Framingham Risk Score) as outcome in the

regression analysis. We will assess the effects of the intervention independently for each of the outcome measures. As many of the baseline co-variates (including sex and age) are related to the prognosis of outcomes, adjustment of pre-defined covariates in the regression analysis might yield in adjusted coefficients which are slightly further from 1.

We will also analyze the changes of SCORE and FRS from baseline to 1-year follow-up and use regression methods to identify predictors of the changes in the scores.

Since patients are recruited into the study during three years from mid-2013 to mid-2016, any change in physicians' prescribing behaviour over the course of the study will be evaluated by comparing prescriptions issued for lipid-lowering and anti-hypertensive medication to participants recruited during the first, second and third years.

Similar statistical methods will be applied for evaluation of the three-year results. At that time point also changes in plaque distributions and IMT variables including differences between intervention and control group will be evaluated.

In long-term, adding risk communication using visualisation of carotid ultrasound results will be compared to routine CVD risk assessment and control within the primary health care setting in hospitalisation due to stroke, myocardial infarctions and revascularisations (at 5-year and 10-year) and reducing overall mortality and cause-specific mortality due to myocardial infarctions and stroke (at 5-year and 10-year) compared to.

Simple survival curves will be established using Kaplan-Meier curves for CVD mortality and morbidity at 5 and 10 years of follow up comparing the intervention to the control group. Thereafter, predictive Cox Proportional Hazard models will be developed to estimate the overall predictive ability of CIMT, plaque and risk factors on CVD morbidity and mortality at 5 and 10 years in the control group and in the intervention group, taking into account time at risk for disease and deaths. Receiver Operating Characteristic Curves (ROC) will be calculated by estimating the Area Under the Curve (AUC) to ensure the highest possible sensitivity and specificity of the predictions. Confirmatory and exploratory statistical modelling will establish relationships between the intervention and intermediate and mediating factors and variables' relative contribution to explain changes in the outcome variables.

Since participants are recruited into the study during the three years from mid-2013 to mid-2016, any change in physicians' prescribing behaviour over the course of the study will be evaluated by comparing prescriptions issued for lipid-lowering and anti-hypertensive medications among participants recruited during the first, second and third years.

As a basis for how to build regression models Causal diagrams (directed acyclic graphs - DAGs) will be established and causal mediation analysis will be undertaken to illustrate the impact of social, gender, psychological and environmental factors by biomedical risk indices on CVD morbidity and mortality.

Health economic modelling studies will be performed for evaluation of cost-effectiveness. Interviews with participants and physicians will be transcribed verbatim and analyzed using Qualitative Content Analysis (52).

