| Secondary outcomes | CVD risk factors, lifestyle, ultrasound results (CIMT, presence of plaque, quantitative and qualitative plaque parameters, presence and degree of significant stenosis), prescriptions and purchases of medications (for the treatment of hypertension, dyslipidemia and diabetes), biochemical markers, and the clinical endpoints myocardial infarction, stroke, revascularization procedures and mortality (all-cause and CVD-specific). |
| Study design | A pragmatic randomized controlled trial nested within routine clinical care |
| Study population | Subjects aged 40, 50 or 60 years, invited as part of their VIP participation within Västerbotten primary healthcare. No:3700 |
| Follow-up period | 10 years from first ultrasound examination |
| Inclusion criteria | 
• age=40 years and first-degree relative with history of CVD at age <60 years• age=50 years and at least one of the following: first-degree relative with history of CVD at age <60 years, smoking, diabetes, hypertension, S-LDL cholesterol ≥ 4.5 mmol/L, abdominal obesity• age=60 years 
Individuals are included in the study only once, at whichever qualifying age point is achieved first.
 |
| Statistical methods | The differences in primary outcomes (SCORE risk and Framingham Risk Score) at one year between the treatment groups will be measured and analyzed using t-test. Differences in changes of SCORE and FRS from baseline to 1-year follow-up will be analyzed with regression methods to identify predictors of the changes in the scores. Survival curves will be established using Kaplan-Meier curves for CVD mortality and morbidity at 5 and 10 years of follow up comparing the intervention to the control group. Predictive Cox Proportional Hazard models will be developed to estimate the overall predictive ability of CIMT, plaque and risk factors on CVD morbidity and mortality at 5 and 10 years. Health economic modelling studies will be performed for evaluation of cost-effectiveness. Interviews with participants and physicians will be analyzed using qualitative content analysis. |
| Evaluation criteria | Primary and secondary outcomes will be evaluated according to Intention-to-treat methodology |

5. Background

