13.1 Power and number of study participants

Calculations were performed to estimate the sample size needed to detect a clinically significant difference between the control group and the intervention group with sufficient power regarding change from baseline to 1-year follow-up in the primary clinical outcome variables, Framingham Risk Score and SCORE, as well as for S-LDL and total cholesterol, systolic blood pressure. Regarding possible detectable change of CIMT from baseline to 3-year follow-up, the available literature reported a mean change of 0.010 ± 0.05 mm/year from the MESA study (48) and in a meta-analysis the progression was 0.000-0.023/year for mean maximal IMT of the common carotid artery (49). For evaluating the effects of the various CIMT variables on the sample-size calculation for a trial, we used a pooled common CIMT progression rate of 0.0147 mm/y (0.044 mm/3 y) with the corresponding SD. For the mean maximum progression rates, we used an estimate of 0.0176 mm/y (50).

Since no data was available from the current population, we hypothesized that a change of CIMT of 0.02 mm would be theoretically possible to detect having standardized protocols for IMT assessment including multiple angles of insonation, anatomic landmarks and automated edge detection software technology as was also recommended in a state of the art paper (15). As the design utilizes randomization, the groups were assumed comparable at baseline, thus no further adjustment for background factors was considered. As a lower limit for power we used a threshold of 0.8, and for significance level we used 0.05. These calculations were based on standard deviations on conventional risk factors derived from VIP 2012 and on CIMT from the Tromsö study (51). The power calculations revealed that an initial total number of 3500 participants with a drop-out rate of 15 % during the study would be sufficient. The limiting factor demanding the largest group size to show a hypothesized detectable effect was CIMT. Thus, the sample size was decided based on that.

| Variabel | Precision | Power | SD | Relevant change Population level | Sample size per group | Minimum detectable change if n=1500/group |
|-------------------------------|-----------|-------|------|-------------------------------------|-----------------------------|--|
| SBP (mmHg) | 0.05 | 0.8 | 16 | 2 | 1500 | 1.7 |
| Serum Cholesterol (mmol/L) | 0.05 | 0.8 | 0.5 | 0.5 | 1500 | 0.05 |

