13.2 Statistical analyses

13.2.1 Dataset and study population

All subjects participating in the study will be included in the analyses. For the drop-out analyses, non-participants (those who did not consent to participation or failed to attend the first ultrasound examination) will be included in the analyses of selection bias for participation, but this evaluation will be based on only a restricted number of variables (sex, age, education, clinical CVD risk factors and lifestyle).

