13.3.2 Drop-outs at the 1-year evaluation

At one year, the study population will be further reduced as a result of exclusions due to significant carotid stenosis (10.2.2), deaths and migration out from the county. Drop-outs will be defined as active withdrawal of consent to participation or failure to attend the 1-year follow-up evaluation after postal invitation and one reminder. Drop-outs will be compared to the other participants regarding risk factors, lifestyle, level of education, and intervention group status at baseline.

13.3.3 Drop-outs at the 3-year evaluation:

SPs will be invited to the 3-year examination irrespective of participation status at the 1-year follow-up, provided they were not excluded according to 10.2.2 or have withdrawn their consent). Therefore, drop-outs at Year 3 will be defined as active withdrawal following the 1 year examination or failure to attend the 3-year follow-up after postal invitation and one reminder. Drop-outs will be compared to the other participants regarding risk factors, lifestyle and educational level as well as intervention group status at baseline.

14 Study administration

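### The 1-year primary SCORE/FRS comparison is an unadjusted t-test among attenders that ignores the baseline score, under an intention-to-treat label and with no stated missing-outcome method

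*Protocol*

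**What the plan says.** The primary test is in Protocol 13.2.3: "The differences in primary outcomes (SCORE risk and Framingham Risk Score) at one year between the treatment groups will be measured and analysed using t-test". The same sentence continues "for a detailed statistical analyses plan see Appendix 4", and that appendix is not among the supplied documents. Section 9.2.3 places the calculation of both scores at the 1-year visit.

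On who is analysed, the evaluation criteria in the Protocol summary (section 4) state: "Primary and secondary outcomes will be evaluated according to Intention-to-treat methodology". Section 13.2.1 adds: "All subjects participating in the study will be included in the analyses".

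On losses, section 13.3.2 says: "Drop-outs will be defined as active withdrawal of consent to participation or failure to attend the 1-year follow-up evaluation". It lists stenosis exclusions, deaths and moves out of the county separately. Its only planned step for drop-outs is a comparison of their baseline characteristics and arm with those of the other participants. The sample size in 13.1 assumes "an initial total number of 3500 participants with a drop-out rate of 15 % during the study would be sufficient".

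Section 13.2.3 also plans a covariate-adjusted linear regression as a sensitivity analysis and an analysis of change from baseline to 1 year aimed at finding predictors. The regression covariates are called pre-defined; sex and age are named, the baseline score is not.

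SAP Amendment 2, Study A (the 6-year evaluation) specifies a repeated-measures model with unstructured covariance, baseline-adjusted ANCOVA, complete-case main analyses and multiple imputation as secondary. It also plans 1- and 3-year SCORE2 comparisons by the same ANCOVA. None of this is tied to the original 1-year SCORE/FRS comparison.

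**The concern.** Someone without a 1-year visit has no 1-year score, and a t-test on those scores leaves that person out. The planned regression and change-score analyses need the same 1-year value, so they leave out the same people. A reader who sees the intention-to-treat label would not learn this from the summary.

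Loss could differ between arms. Before the 1-year visit, only intervention participants and their physicians are sent the ultrasound result. Section 12.2.1 also describes a nurse call, a 6-month repeat of the result and a 9-month reminder for that arm; 12.3 describes no equivalent contacts for controls. Section 8.4 accepts that disclosure may cause anxiety. If higher-risk people stay away more often in the intervention arm, attenders there look better than the arm as a whole and the bias favours the intervention. The reverse pattern would hide an effect. Equal attendance rates would not exclude either.

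The plan already holds a strong predictor of the 1-year score, the baseline score, and the stated primary test does not use it.

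**Working it through.** **Inputs from Protocol 13.1 and 13.2.3.** 3500 participants in total, two equal arms, 15% drop-out over the study, two-sided 5% level, power 0.8. SD 6.60 for FRS and 1.40 for SCORE. Stated relevant changes 1 and 0.5; stated minimum detectable changes 0.7 and 0.143 at 1500 per group.

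**Reproducing the plan.** 1500 / 0.85 = 1765 per group, 3530 in total, against 3500 stated. In reverse, 3500 × 0.85 / 2 = 1487.5 per group, against 1500. The minimum detectable change is SD × (1.960 + 0.842) × √(2/1500): 0.143 for SCORE and 0.675 for FRS, matching 0.143 and 0.7. So the plan itself expects to analyse about 1500 attenders per arm.

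**People without a score.** At 15% loss, 0.15 × 3500 = 525 (0.15 × 3532 = 530 on the number actually included).

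**Power is not the issue.** At 1487 per arm, power for a 1-point FRS difference is 0.985.

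**Bias formula.** In each arm, the attenders' mean equals the full mean minus L × gap, where L is the proportion lost and gap is the mean of those lost minus the mean of attenders. With equal L, the bias in the arm difference is L × (difference in gaps between arms). Equal gaps cancel.

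**Scenario (assumed).** No true effect. Loss is unrelated to baseline score in one arm and rises with it in the other by 0.3 or 0.5 log-odds per SD. The baseline to 1-year correlation is 0.8.

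Integrating the logistic loss over a normal baseline score gives a baseline gap of 0.297 or 0.484 SD at 15% loss, and 0.298 or 0.491 SD at 7.5%. Then bias = L × gap × 0.8 × 6.60. The SE is 6.60 × √(2/1487.5) = 0.242 at 15% loss and 6.60 × √(2/1618.75) = 0.232 at 7.5%. The false-positive rate is the chance that a normal estimate centred on the bias passes ±1.96 SE.

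| Loss | Log-odds per SD | Bias, direct (FRS) | False positives, direct | Simulated range |
|---|---|---|---|---|
| 15% | 0.3 | 0.15 × 0.297 × 5.28 = 0.235 | 16% | 0.24 to 0.37 points, 17% to 34% |
| 15% | 0.5 | 0.15 × 0.484 × 5.28 = 0.383 | 35% | (as above) |
| 7.5% | 0.3 | 0.075 × 0.298 × 5.28 = 0.118 | 8% | 0.12 to 0.20 points, 9% to 14% |
| 7.5% | 0.5 | 0.075 × 0.491 × 5.28 = 0.194 | 13% | (as above) |

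The direct and simulated figures agree within simulation error. For SCORE, bias and SE both scale by 1.40/6.60, so 15% loss gives about 0.05 to 0.08 points with the same error rates.

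**What removes the bias in this scenario.**
- Same loss model in both arms (0.5 per SD, 15%): bias about 0, false positives 4% to 5%, even with the t-test.
- Simple change score among attenders: bias 0.06 to 0.10, false positives 6% to 10%.
- Regression on the baseline score among attenders: bias about 0, false positives about 5%, and SE = 0.242 × √(1 − 0.8²) = 0.145.

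Most of the gain therefore comes from using the baseline score. Scoring the non-attenders adds less here, because loss was assumed to depend only on that score.

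**The case against.** The strongest objection is that 13.2.3 is headed as a summary and defers to Appendix 4, while Amendment 2 confirms that the original plan describes the study populations. A missing-data rule may well be there. This stands: the point can say only that the supplied text gives none.

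Second, 15% is a rate over the whole study, in a sample size driven by 3-year CIMT. The pilot had complete risk-factor data for 81 of 95 people at three years, a shortfall of 14.7%, so 1-year loss may be lower. This also stands, and is why 7.5% is shown.

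Third, the planned regression could remove most of the problem if the baseline score is among its covariates. That cannot be checked, and it is a sensitivity analysis, not the primary one.

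Fourth, the Protocol amendment for the 6-year follow-up says the primary evaluation is complete and published. Replacing a prespecified test with results known would be post hoc. This stands and shapes the fix.

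Stronger readings are tempting but not supported:
- A reader might infer that any score-related loss biases the t-test. It does not; only a between-arm difference in selection does.
- A reader might infer that the intention-to-treat and all-participants statements cannot be met at all. Intention-to-treat can mean analysis by assigned arm, and 13.2.1 contrasts participants with non-participants; neither passage promises a score for every missing visit.
- A reader might infer that the published result is biased. The documents give no evidence of differential selection.

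**Conclusion.** The concern holds in limited form. In the supplied text, the 1-year primary comparison is an attenders-only, unadjusted t-test under an intention-to-treat label, with no missing-outcome method, although a better predictor-based analysis is available from data already held. Under the assumed one-arm selection, the bias of 0.24 to 0.37 FRS points at 15% loss is 24% to 37% of the 1-point change the plan calls relevant. At 7.5% loss it is 12% to 20%. With equal selection in both arms it is zero.

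These sizes rest on an assumed correlation, selection strength and 1-year loss rate; actual size and direction are unknown. Conditioning on the baseline score does not cure loss that depends on the unseen 1-year score itself. A related departure is not covered here: people are randomised before the first ultrasound (12.1), and those who never attend it become non-participants (13.3.1).

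**What to change.** In Protocol 13.2.3, and in Appendix 4 if it is silent:

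1. Define the set as all scanned participants not excluded under 10.2.2, by assigned arm, whether or not they attended at 1 year.
2. Estimate the 1-year difference with a model that conditions on the baseline score. Baseline-adjusted ANCOVA is the simple form, but alone it still uses attenders only. The repeated-measures model already specified in Amendment 2, fitted to the baseline, 1-year and 3-year scores, also lets 1-year non-attenders contribute. Section 13.3.3 invites them at year 3 regardless of 1-year attendance, and controls receive results only after that follow-up.
3. Report deaths separately by arm.
4. Add a delta-adjusted sensitivity analysis that shifts non-attenders' scores by 0.1 to 0.5 SD in one arm.
5. Describe the attenders-only t-test as a complete-case analysis.

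Because the 1-year result is published, leave the prespecified t-test as reported and label the new estimate supplementary. Apply the same approach to the 1- and 3-year SCORE2 comparisons in Amendment 2. Those already adjust for baseline, so the change there is to include non-attenders and add the delta analysis.

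The cost is some wording and one further model on data already collected, an explicit missing-at-random assumption, and a slightly more complex analysis to explain.

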6.1 Objective

To assess the impact of a visual image and pictorial report, seen and discussed by both physician and patient, for improving guideline adherence and patient perception and understanding of the CVD risk and consequent motivation for prevention. The extent of the impact is assessed by differences between randomization groups in Framingham Risk Score and SCORE as well as changes in these scores after one and three years. Differences between groups will also be evaluated by risk factor assessment and a further scan after three years to determine disease progression, and a comparison of the prevalence of acute events and mortality at five and 10 years.

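### The primary 1-year comparison of SCORE and FRS is an unadjusted t-test; ANCOVA on the baseline score, already planned elsewhere in the trial, would give narrower intervals at almost no cost

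*Protocol*

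**What the plan says.** Protocol section 13.2.3 states that the two primary outcomes will be compared "at one year between the treatment groups will be measured and analysed using t-test", and the Summary (section 4) says the same. Section 13.2.3 plans similar methods at three years.

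The baseline score and other covariates appear in three further places:

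- **Sensitivity analysis.** "In sensitivity analyses, we will conduct a linear regression covariate-adjusted analysis" (section 13.2.3). The text mentions sex and age as examples of baseline covariates and refers to Appendix 4 for detail. It adds that adjustment "might yield in adjusted coefficients which are slightly further from 1".
- **Change from baseline.** "We will also analyze the changes of SCORE and FRS from baseline to 1-year follow-up" (section 13.2.3). The Summary gives the purpose: "Differences in changes of SCORE and FRS from baseline to 1-year follow-up will be analyzed with regression methods to identify predictors". Section 6.1 also lists, as a measure of impact, group differences in the scores "as well as changes in these scores after one and three years".
- **Power.** Section 13.1 relies on randomisation to make the groups comparable, "thus no further adjustment for background factors was considered". It describes the calculation as one for change to one year, takes the risk-factor SDs from VIP 2012, and says that CIMT determined the sample size.

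SAP Amendment 2, Study A, uses ANCOVA adjusted for the corresponding baseline value for FRS and SCORE2 at 6 years, with and without sex and educational level. It uses the same ANCOVA for SCORE2 at 1 and 3 years. It also plans a mixed model over baseline, 1, 3 and 6 years.

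**The concern.** A t-test on the 1-year scores leaves in the error term all the stable variation between people. That variation is built into the design: both sexes are enrolled, at ages 40, 50 and 60. The baseline risk factors are measured at the VIP visit, before randomisation, so the baseline score is a legitimate covariate and is already held. The reason given in section 13.1 for not adjusting supports the validity of the t-test but does not address the width of its interval.

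On the supplied text, SCORE and FRS at 1 and 3 years are the exception. SCORE2 at those visits, and FRS at 6 years, are to be baseline-adjusted. A reader comparing intervals across visits or scores would be comparing different methods.

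Two wording points go with this. In a linear regression of a continuous score the null value of a coefficient is 0, not 1, and the expected benefit of adjustment in a randomised trial is a smaller standard error, not a larger coefficient. Section 13.1 also speaks of change while section 13.2.3 tests level, and section 13.1 does not say which of the two its SDs describe.

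**Working it through.** **Inputs.** From the section 13.1 table: SD 1.40 for SCORE and 6.60 for FRS; relevant change 0.5 and 1; 1500 per group; power 0.8; significance level 0.05, two-sided by section 13.2.3. The SDs are taken as SDs of level. The correlation r between baseline and 1-year score is not in the documents; it is assumed, and shown over a range.

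**1. The plan's own figures.** SE = SD × √(2/1500).

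- SCORE: 1.40 × 0.03651 = 0.0511
- FRS: 6.60 × 0.03651 = 0.2410

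The minimum detectable difference is (1.960 + 0.8416) × SE = 2.8016 × SE, which gives 0.143 for SCORE (table 0.143) and 0.675 for FRS (table 0.7, to one decimal). The table therefore follows the unadjusted two-group formula.

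**2. Adequacy of the t-test.** Sample size per group for power 0.80 is 2 × (2.8016 × SD / d)².

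- SCORE, d = 0.5: 123.07, so 124
- FRS, d = 1: 683.8, so 684

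At 1500 per group, power is above 0.999 for SCORE and 0.986 for FRS.

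**3. Effect of using the baseline.** Relative to the t-test, and with equal variance at both visits, the SE factor is √(2(1 − r)) for a change-score comparison and √(1 − r²) for ANCOVA. Their ratio, ANCOVA to change, is √((1 + r)/2).

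| r | Change factor | ANCOVA factor | ANCOVA SE below change SE |
|---|---|---|---|
| 0.5 | 1.000 | 0.866 | 13.4% |
| 0.6 | 0.894 | 0.800 | 10.6% |
| 0.8 | 0.632 | 0.600 | 5.1% |
| 0.9 | 0.447 | 0.436 | 2.5% |

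**4. 95% CI half-widths** (1.96 × SE × factor, 1500 per group). The t-test gives 0.100 for SCORE and 0.472 for FRS.

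| r | SCORE change | SCORE ANCOVA | FRS change | FRS ANCOVA |
|---|---|---|---|---|
| 0.6 | 0.090 | 0.080 | 0.422 | 0.378 |
| 0.8 | 0.063 | 0.060 | 0.299 | 0.283 |
| 0.9 | 0.045 | 0.044 | 0.211 | 0.206 |

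A simulation with 1500 per group and SD 1.40 agreed. The SCORE half-width was 0.100 unadjusted, and 0.087, 0.072 and 0.044 adjusted at r = 0.5, 0.7 and 0.9.

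**The case against.** The strongest reply is that nothing is wrong with the primary test. It is unbiased under randomisation and amply powered for the protocol's own relevant changes, and CIMT, not the scores, set the sample size. That stands. A reader might infer that the t-test is biased, invalid or underpowered, or that the 1-year conclusion is in doubt; the documents support none of these.

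A reader might also infer that the plan ignores the baseline score. It does not. A change analysis is planned, and section 6.1 counts change among the measures of impact. Against a change score the gain is small. But the Summary and section 13.2.3 give that analysis the purpose of finding predictors, and it is not the primary test.

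Appendix 4 and any SAP amendment before Amendment 2 were not supplied. The predefined covariates may include the baseline score, in which case the sensitivity regression is already the ANCOVA proposed here. So it cannot be said that baseline adjustment was never planned, only that the supplied text does not make it primary.

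Much is also settled already. The primary evaluation is published, as are the 1- and 3-year group differences for every Study A outcome except SCORE2, and Amendment 2 plans a mixed model across visits. Under that amendment, however, group differences in FRS are to be tested and presented only at 6 years. Finally, Amendment 2 itself treats comparisons after year 3 as post-trial, because the controls then received their ultrasound results. A 10-year ANCOVA would therefore not be a more precise version of the primary test.

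**Conclusion.** The point holds as a matter of precision and consistency, not of bias. With 1500 per group and the section 13.1 SDs read as level, ANCOVA on the baseline score would reduce the standard error of the primary comparison by 20% at r = 0.6 and by 56% at r = 0.9. If the comparator is a change score, the reduction is 10.6% to 2.5%. The correlation is an assumption, so the size is uncertain; the direction is not.

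The level reading is supported by the source of the SDs, a survey of people in the years they turn 40, 50 and 60, but section 13.1 does not state it. If the SDs are of change, the power and half-widths given here for the t-test do not carry over. The error about the null value is definite, but it alters no planned calculation.

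**What to change.** - **SCORE and FRS at 1 and 3 years.** Keep the published prespecified result. Report beside it the ANCOVA of the follow-up score on arm and the same baseline score, with and without sex and educational level as in SAP Amendment 2. Label it as added later only if neither Appendix 4 nor an earlier SAP amendment prespecified it.
- **10-year visit.** The supplied documents give no method for the scores. State the same ANCOVA, and describe the result as a post-trial comparison.
- **Section 13.2.3.** Replace the sentence about coefficients moving away from 1 with: adjustment is expected to reduce the standard error; the null value is 0.
- **Section 13.1.** As a minor clarification, state whether each tabulated SD is of level or of change.

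The cost is one regression per score and visit, fitted with and without the extra covariates, a short SAP paragraph and two wording corrections. No new data are needed.
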